5. GENERAL METHODOLOGY AND CONVENTIONS

The primary analysis will be performed when all randomized subjects have either completed their 16-week study participation period or withdrawn early or should the study be stopped prematurely due to any reason, and the database is released. *An interim analysis may be performed for making internal business decisions regarding future study planning. In that case, before any interim analysis is instigated, the details of the objectives, decision criteria, dissemination plan and method of maintaining the study blind as per Pfizer's SOPs will be documented and approved in the IRC charter.*

5.1. Hypotheses and Decision Rules

Statistical inference will be made on the primary endpoint: Proportion of participants achieving PASI 90 (90% or greater improvement from Baseline) at Week 16 based on an analysis of the Primary Estimand Endpoint Set. The global null hypothesis is that there is no difference between any arm of PF-06826647 and placebo arm. The alternative hypothesis is that one of the PF-06826647 arms being tested is superior to the placebo arm at Week 16. The study will be considered positive, if this null hypothesis is rejected.

Since test statistic corresponding to each of the PF-06826647 arms are independent with each others satisfying the distributional assumption about the use of Hochberg step-up procedure, the familywise error-rate will be controlled in strong sense at the 1-sided 0.05 level for these tests with a Hochberg step-up procedure (Hochberg, A sharper Bonferroni procedure for multiple significance testing 1988)³ (Hochberg and Tamhane, Multiple Comparison Procedures 1987)⁴ (Marcus, Peritz and Gabriel 1976). The p-values from the 3 comparisons will be ordered from smallest to largest, $p[1]$, $p[2]$, and $p[3]$. Testing will begin with the largest p-value, $p[3]$, if significant at the 0.05 level that comparison and all other comparisons will be declared significant. If it is not significant, $p[2]$ will be compared to an alpha of 0.05/2, if $p[2] \leq 0.05/2$ it and all remaining hypotheses will be declared significant. If not significant, the process will continue using 0.05/3.

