9.4.1. Efficacy Analyses

Endpoint	Statistical Analysis Methods
Primary and key secondary: PASI 90 and PASI 75 at Week 16	A landmark analysis of the composite endpoint; achieving a PASI 90 response (a score of 90% improvement from Baseline) without prohibited medication, while remaining on study and providing data. The analysis will use the mITT analysis set. Based on the definition of the composite endpoint all participants in the mITT set will have a response for all visits (ie, there is no missing data). The proportions responding and the risk difference between treated arms and their corresponding placebo arm will be analyzed using an unconditional exact method: risk differences and corresponding 2-sided unconditional exact 90% confidence intervals will be computed using the Chan and Zhang (1999) method. Multiplicity adjustment will be utilized; details of multiplicity adjustment will be provided in the SAP.

Other continuous secondary endpoints at time points specified in the [Schedule of Activities](#) including; absolute PASI, change from baseline PASI, percent change from baseline PASI, absolute and change from baseline Itch Severity Score, absolute and change from baseline Psoriasis Symptom Inventory will be analyzed as described for the E2 estimand along with descriptive statistics and possibly graphical displays. No adjustments for multiplicity will be made for these endpoints.

Other binary secondary endpoints at time points specified in the [Schedule of Activities](#) including, PASI 50, PASI 100, PGA of clear or almost clear and proportions of participants achieving a Psoriasis Symptom Inventory Score of 0 or 1 will be analyzed as described for the primary estimand along with descriptive statistics and possibly graphical displays. No adjustments for multiplicity will be made for these endpoints.

CCI [REDACTED]

All endpoints in Extension Treatment Period will be analyzed with descriptive statistics and graphical displays when appropriate. Details of the analyses of the Investigational Treatment Period and Extension Treatment Period will be included in the Statistical Analysis Plan (SAP).

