6. ANALYSES AND SUMMARIES

Analysis will be done pairwise between each of the PF-06826647 treated groups and the placebo group. An analysis with point estimates of the difference, the associated 90% confidence intervals and p-values will also be reported.

A summary of analyses for clinical efficacy endpoints is provided in [Appendix 1](#). Visit windows to be used for all efficacy analyses and some relevant safety analyses are detailed in [Appendix 2.1](#).

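### The protocol promises multiplicity adjustment for PASI 75 at Week 16, but the SAP defines an adjustment for PASI 90 only

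*SAP*

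**What the plan says.** The efficacy table in protocol 9.4.1 has one row labelled "Primary and key secondary: PASI 90 and PASI 75 at Week 16". For that row it states: "Multiplicity adjustment will be utilized; details of multiplicity adjustment will be provided in the SAP". Below the table, two groups of other secondary endpoints are exempted: "No adjustments for multiplicity will be made for these endpoints". The exempt binary group is listed as "PASI 50, PASI 100, PGA of clear or almost clear and proportions of participants achieving a Psoriasis Symptom Inventory Score" and so on. PASI 75 is in neither group.

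SAP 5.1 opens with "Statistical inference will be made on the primary endpoint: Proportion of participants achieving PASI 90 (90% or greater improvement from Baseline) at Week 16" and then says that "the familywise error-rate will be controlled in strong sense at the 1-sided 0.05 level for these tests with a Hochberg step-up procedure". Those tests are the PASI 90 dose comparisons.

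PASI 75 is handled elsewhere in the SAP. Section 5.2.1 says key binary endpoints are tested by the Chan and Zhang method and names PASI 75 among the key binary endpoints. Section 6.2.1 gives proportions, risk differences and 90% intervals at the scheduled visits. Section 6, which covers each active dose against placebo, adds: "An analysis with point estimates of the difference, the associated 90% confidence intervals and p-values will also be reported". None of these sections adjusts PASI 75 or singles out Week 16 for it.

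**The concern.** PASI 75 is the only endpoint the objectives tables label key secondary, and the study is meant to support dose selection. A reader of the protocol will expect the Week 16 PASI 75 comparisons to carry some control of error across the four doses. A reader of the SAP will find four p-values and four 90% intervals with none. A 90% two-sided interval that excludes zero on the favourable side corresponds to a one-sided 5% test, so each dose can easily be read as a claim at that level. The chance of at least one false dose claim would then be well above the 5% the sponsor chose for PASI 90.

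**Working it through.** **1. Is PASI 75 covered anywhere in the SAP?** The only other multiplicity text is SAP Appendix 3, a Hochberg scheme for six unnamed null hypotheses. Four doses on one endpoint make 4 comparisons, and four doses on two endpoints make 4 × 2 = 8. Neither is six. SAP 5.1 uses yet another count: "The p-values from the 3 comparisons will be ordered from smallest to largest". The appendix therefore cannot be taken to supply the missing PASI 75 rule.

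**2. Inputs for the size.**
- Randomised numbers (protocol 4.1): placebo 40; 50 mg 20; 100 mg 20; 200 mg 40; 400 mg 40.
- Level (SAP 5.1): one-sided 0.05, critical value 1.645.
- The documents give no PASI 75 response rate, so a common rate of 3% to 50% is assumed where one is needed.

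**3. Nominal error with all four doses ineffective.** The comparisons share one placebo arm, so the test statistics for doses i and j have correlation √[nᵢ/(nᵢ+40) × nⱼ/(nⱼ+40)]:
- 50 with 100 mg: √(20/60 × 20/60) = 0.333
- a low with a high dose: √(20/60 × 40/80) = 0.408
- 200 with 400 mg: √(40/80 × 40/80) = 0.500

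With multivariate normal statistics, 1 − P(all four Z < 1.645) = **15.3%**. For comparison, independence would give 1 − 0.95⁴ = 18.5%, and the Bonferroni bound is 4 × 5% = 20%.

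**4. Allowing for the exact test.** The planned test is unconditional and exact, and is conservative in small samples. I enumerated a one-sided unconditional exact test (score ordering, p-value maximised over the common rate) at the randomised numbers. Over nine common rates from 3% to 50%, the chance of at least one rejection at 0.05 was:

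| Common rate | At least one false rejection |
|---|---|
| 3% | 12.0% |
| 5% | 11.7% |
| 8% | 10.5% |
| 10% | 11.6% |
| 15% | 12.8% |
| 20% | 12.3% |
| 30% | 12.2% |
| 40% | 12.6% |
| 50% | 12.3% |

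That is **about 12%** (10.5% to 12.8%).

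**5. Only the two low doses ineffective.** With correlation 0.333, 1 − P(both Z < 1.645) = **9.2%** nominally. The exact enumeration gives about 6% to 7%.

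**6. Effect of adjusting.** Hochberg over the four PASI 75 p-values compares the largest with 0.05, then the next with 0.05/2 = 0.025, 0.05/3 = 0.0167 and 0.05/4 = 0.0125. Simulating two million sets of statistics with the correlations in step 3 gives **about 4.4%** under the global null.

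**7. Would a gate on PASI 90 work?** Protocol 4.3 projects PASI 90 rates of 3%, 13%, 47% and 83% for 50, 100, 200 and 400 mg, and protocol 9.2 assumes 5% on placebo. At those rates, the exact test at one-sided 0.05 rejects all four PASI 90 nulls about 1.2% of the time. A rule that tests PASI 75 only after all four rejections would almost never open.

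**The case against.** The strongest reply is that SAP 5.1 makes PASI 75 supportive by confining inference to PASI 90. The objectives tables say binary secondary endpoints will be analysed descriptively as well as under estimand E1. Protocol section 9 lets the SAP modify the protocol and requires an amendment only for major changes to the primary endpoints or their analyses. On that view the sponsor was free to narrow the commitment.

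Part of this stands. No document sets a success rule for PASI 75, so a reader who infers that the plan itself declares each dose at one-sided 0.05, and so has a 15% false-claim rate, goes further than the text. The percentages apply only if the p-values are used as claims. The 15.3% is also asymptotic and assumes that no dose works, whereas the sponsor expects 200 and 400 mg to be effective.

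The reply does not close the gap. The SAP nowhere says the PASI 75 adjustment was dropped, and its change history lists no such change. The protocol delegated the details of the adjustment, and silence does not supply them.

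A second reply is that three comparisons on two endpoints would make the six of Appendix 3. That is arithmetically possible, but there are four doses and the appendix names no endpoint. Correcting the family-size count would still leave SAP 5.1 limited to PASI 90.

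A reader might also add the other scheduled visits to the error count. The protocol's commitment is to Week 16, so they do not belong in it.

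**Conclusion.** The point holds. The protocol commits the key secondary endpoint at Week 16 to multiplicity adjustment, and the SAP provides none. If the PASI 75 p-values are read as claims, the chance of at least one false dose claim under the global null is 15.3% nominally, and about 12% with an exact test of the planned type over assumed common rates of 3% to 50%. The sponsor's own level is 5%. With only the low doses ineffective, the nominal figure is 9.2%. These figures rest on the planned 40/20/20/40/40 randomisation and one-sided 0.05 per comparison. The primary PASI 90 conclusion is untouched, and the issue is separate from the inconsistent counts of three and six in the PASI 90 procedure. It should be corrected before the Week 16 results are interpreted.

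**What to change.** In SAP 5.1, add PASI 75 at Week 16 as a second family. Apply the same Hochberg step-up to its four dose comparisons at one-sided 0.05 and leave the PASI 90 procedure unchanged. State that error is controlled across doses within each endpoint, not jointly across the two endpoints. Do not make the PASI 75 tests depend on rejecting all four PASI 90 nulls. Label PASI 75 p-values at every other visit nominal.

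If the sponsor means PASI 75 to be supportive, the alternative is to say so in the SAP, label all its p-values nominal, and reconcile protocol 9.4.1.

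The first option costs a paragraph in SAP 5.1 and makes PASI 75 claims at individual doses somewhat harder to reach. The second costs a sentence in the SAP and a matching change to the protocol, and gives up controlled PASI 75 claims.

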2.2. Study Design

This is a Phase 2b, randomized, double blind, placebo controlled, parallel group, multicenter study in participants with moderate to severe plaque psoriasis. After a screening period of - up to 6 weeks, eligible participants will be randomized in a 2:1:1:2:2 ratio such that participants will receive placebo or either one of four PF-06826647 daily dose levels (50 mg, 100 mg, 200 mg or 400 mg) every day during the Investigational Treatment Period for 16 weeks in a blinded fashion. All participants completing the 16 week Investigational Treatment Period will continue on to a 24 week non-placebo controlled Extension Treatment Period with double blind oral daily treatment, if per the Investigator judgment the participant is compliant with study procedures and continued participation presents no safety risks. The participants continuing into the Extension Treatment Period that were originally randomized to the 200 mg and 400 mg treatment groups will continue on their respective doses, while those randomized to one of the other treatment groups (including placebo) will be randomly assigned (at study baseline) to receive either 200 mg or 400 mg during the Extension Treatment Period. Participants who discontinue prior to Week 16 visit will enter the Follow-Up period and will not be eligible for the Extension Period.

Approximately 160 participants (40 participants in each of the following arms: placebo, 200 mg, and 400 mg; and 20 participants in each of the following arms: 50 mg and 100 mg) will be randomly assigned to a treatment group in order to ensure a minimum of 128 evaluable participants completing Week 16 (assuming a 20% dropout rate).

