Appendix 3. Statistical Methodology Details

Hochberg Testing Procedure

Consider testing null hypotheses H_{01}, \dots, H_{06} and let $p_i, i=1, \dots, 6$ denote the corresponding 1-sided p-values from the individual pairwise comparisons against the placebo arm prior to multiplicity adjustment. Furthermore, let $[1], \dots, [6]$ denote the order of the p-values so that $p[1] \leq p[2] \leq \dots \leq p[6]$. The procedure starts with the largest p-value $p[6]$ as follows:

1. If $p[6] < \alpha$ reject all null hypotheses, otherwise go to next step.
2. If $p[5] < \alpha/2$ reject hypotheses $H_{0[1]}$ through $H_{0[6]}$, otherwise go to next step.
3. If $p[k] < \alpha/(6-k+1)$, reject hypotheses $H_{0[1]}$ through $H_{0[k]}$.
4. If $p[1] < \alpha/6$, reject $H_{0[1]}$, otherwise stop and do not reject any hypotheses.

Alternatively, the unadjusted raw p-values can be read into Proc Multtest and adjusted using the HOC option in SAS's PROC MULTTEST.

```
data pvals;  
  Input Test$ Raw_P;  
Datalines;  
Test1 .xxxxx  
Test2 .xxxxx  
.....  
Test6 .xxxxx  
;  
Proc multtest pdata=pvals hoc out=new;  
run;
```

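### The Hochberg rule that decides a positive study is written for three tests in SAP 5.1 and six in Appendix 3, while four doses are tested; step 2 of the appendix also rejects a hypothesis that has just failed

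*SAP*

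**What the plan says.** SAP 2.2 randomises participants to placebo or "one of four PF-06826647 daily dose levels (50 mg, 100 mg, 200 mg or 400 mg"). SAP 6 states: "Analysis will be done pairwise between each of the PF-06826647 treated groups and the placebo group". That makes four dose-versus-placebo tests.

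SAP 5.1 promises strong control of familywise error at one-sided 0.05 and calls the study positive if the global null is rejected. It then specifies Hochberg for three p-values: "The p-values from the 3 comparisons will be ordered from smallest to largest". The thresholds are 0.05, 0.05/2 and 0.05/3. Its reason for using Hochberg begins: "Since test statistic corresponding to each of the PF-06826647 arms are independent with each others".

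Appendix 3 sets out the same procedure for six pairwise comparisons with placebo: "The procedure starts with the largest p-value $p[6]$ as follows". Its last threshold is α/6, and its PROC MULTTEST template has six rows. Step 2, reached only when p[6] has failed, says for p[5] < α/2: "reject hypotheses $H_{0[1]}$ through $H_{0[6]}$, otherwise go to next step".

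On PASI 75, the row of Protocol 9.4.1 that names both PASI 90 and PASI 75 at Week 16 says: "Multiplicity adjustment will be utilized; details of multiplicity adjustment will be provided in the SAP". SAP 5.1 says only: "Statistical inference will be made on the primary endpoint".

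**The concern.** The two versions set different bars for the same decision, and neither matches the four planned tests. Nothing in either document names three doses to test or a family of six. Protocol 9.4.1 leaves the detail to the SAP, and the sample-size text in Protocol 9.2 says Bonferroni without giving a divisor. The count is therefore open, and could be settled after the data are seen.

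Step 2 is a separate fault. It cannot make a negative study positive, because other hypotheses are already being rejected at that point. It can attach a claim of superiority to a dose that failed its own test, in a trial whose stated purpose is dose selection.

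The independence statement is a wrong reason for a usable method. The status of PASI 75 is a smaller loose end.

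**Working it through.** **Inputs.** Randomised arms of 40 placebo, 20 (50 mg), 20 (100 mg), 40 (200 mg) and 40 (400 mg), from Protocol 4.1. Placebo rate 5% and effect 35 points, hence 40% on active, from Protocol 9.2. Projected PASI 90 rates of 3%, 13%, 47% and 83%, from Protocol 4.3. The 25% rate and the 5/40/40/40% scenario below are assumptions.

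**1. Thresholds.** Hochberg with m tests compares p[k] with 0.05/(m − k + 1) and, at the largest k that passes, rejects H0[1] to H0[k].

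| Rule | p[1] | p[2] | p[3] | p[4] |
|---|---|---|---|---|
| Three tests (5.1) | 0.0167 | 0.025 | 0.05 | none |
| Four tests (design) | 0.0125 | 0.0167 | 0.025 | 0.05 |
| Six tests (Appendix 3), first four positions | 0.0083 | 0.01 | 0.0125 | 0.0167 |

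**2. Does 5.1 hold 5% for what it describes?** Yes, for three tests. Normal-theory simulation gives 0.0495 if independent and 0.0443 at correlation 0.5. With four tests and 0.05/3 as the strictest threshold, the bound is 4 × 0.05/3 = 0.0667, and simulation with the shared placebo gives 0.0567. Four-test Hochberg gives 0.0438 with the shared placebo and 0.0492 if independent.

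**3. Correlation.** The formula is √[ni/(ni+n0)] × √[nj/(nj+n0)], with n0 = 40.
- 50 and 100 mg: √(20/60) × √(20/60) = 0.33
- A low and a high dose: √(20/60) × √(40/80) = 0.41
- 200 and 400 mg: √(40/80) × √(40/80) = 0.50

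**4. Familywise error with an exact test.** One-sided unconditional exact p-values (score ordering, maximised over the nuisance rate), 1,000,000 trials per scenario. Placebo and ineffective doses are at 5%.

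| Scenario | Three-test thresholds on the three smallest of four | Four-test |
|---|---|---|
| No dose works | 3.8% | 3.1% |
| Only 400 mg works (40%) | 5.6% | 2.8% |
| 200 and 400 mg work (47%, 83%) | 7.0% | 3.3% |

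If 0.05/3 is instead reused as the last step on all four p-values, the global-null rate is 3.3% at a 5% base rate and at most 4.7% at the base rates run with these arm sizes. With the six-test thresholds it is 0.1% to 2.6% over common rates from 2% to 50%.

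**5. Effect on the verdict.** Probability of a positive study:

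| Scenario | 3 tests | 4 tests | 6 tests |
|---|---|---|---|
| Projected rates | about 100% | about 100% | about 100% |
| One 40-patient dose at 40% | 97.3% | 96.7% | 94.5% |
| One 40-patient dose at 25% | 67.4% | 64.1% | 56.5% |

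Two results that change the verdict when no other dose is significant:
- Placebo 1/40, dose 7/40: p = 0.0165. Positive under three tests, negative under four and six.
- Placebo 2/40, dose 9/40: p = 0.0124. Positive under three and four, negative under six.

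At the projected rates, 100 mg is declared significant in about 22%, 17.5% and 10.5% of trials under three, four and six tests.

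**6. Step 2.** Step 3 of the appendix at k = 5 has the threshold α/(6 − 5 + 1) = α/2, the same as step 2, but rejects only through H0[5]. The appendix therefore contradicts itself. Carried to four tests, the fault reads: p[4] > 0.05 and p[3] ≤ 0.025 rejects all four.

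| Scenario, placebo 5% | 50 mg declared superior, step 2 as written | Correct rule |
|---|---|---|
| Projected 3/13/47/83% | 17.6% | 1.3% |
| 5/40/40/40% | 89% | 4% |

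**The case against.** The strongest reply is that this is drafting, with little practical effect.

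- **Error inflation depends on the reading.** It needs all four doses to be tested and the largest p-value then set aside. With a fixed set of three doses (50 mg dropped), familywise error is 2.6%, 3.7% and 3.9% in the three scenarios of the second table. Reusing 0.05/3 on four p-values is also benign with the exact test. At 32/16/32 completers, the 5.6% falls to 4.5%, although the 7.0% becomes 7.5%. This stands as a limit on size. It does not say which reading applies, and the SAP does not either.
- **PROC MULTTEST would correct itself.** Its HOC option adjusts for the number of p-values supplied, so four p-values give the right answer without the step 2 fault. True, but the SAP offers it only as an alternative, with a six-row template.
- **Step 2 is probably a slip in one subscript.** SAP 5.1 and step 3 both carry the correct logic. That is likely, and the 17.6% and 89% come from carrying the slip to four tests. It still leaves two incompatible instructions in the appendix that defines the method.
- **Independence and PASI 75 are minor.** Agreed. Hochberg holds its level under this positive dependence. Protocol 9 lets the SAP modify the protocol, so PASI 75 needs only a clear statement.

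**Conclusion.** The concern holds. The rule that decides a positive study exists in two versions, and neither fits four tests. Nothing else in the documents settles the count.

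The consequence depends on the data. At the projected rates the positive-study verdict does not move. At the planned 35-point effect in a single 40-patient dose it moves by 97.3 − 94.5 = 2.8 percentage points between three and six tests. At an assumed 25% rate it moves by 67.4 − 56.5 = 10.9 points. The excess error of 5.6% to 7.0% is the worst reading of 5.1. The step 2 figures apply if that step is followed literally with four tests. All simulated rates rest on a 5% placebo response unless another base rate is given, and on the randomised arm sizes unless completers are named.

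The rule should be settled before unblinding, because it governs both the study verdict and the dose-level claims.

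**What to change.** 1. In SAP 5.1, Appendix 3 and the PROC MULTTEST template, use four p-values. Compare p[4] with 0.05, p[3] with 0.025, p[2] with 0.0167 and p[1] with 0.0125.
2. Rewrite step 2 of Appendix 3 so that, once p[4] has failed, p[3] ≤ 0.025 rejects H0[1] to H0[3] only.
3. Replace the independence sentence with a statement that the test statistics are positively correlated through the shared placebo arm (about 0.33 to 0.50), and that Hochberg controls familywise error under this dependence.
4. For PASI 75 at Week 16, bring Protocol 9.4.1 and SAP 5.1 into line. Either label it descriptive in both, or place it in a procedure shown to give strong control across both endpoints. A per-dose gate that reuses the full alpha would not be enough.

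The cost is wording in two SAP sections, two fewer template rows and one sentence on PASI 75. Data, sample size and conduct do not change.
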